### **Revision History**

Revision #	Date	Description
01	10 May 2016	Initial release

## 1 CLINICAL STUDY SYNOPSIS

STUDY TITLE	Utilizing Novel dipole density Capabilities to Objectively Visualize the Etiology of Rhythms in Atrial Fibrillation (UNCOVER-AF)
DEVICE NAME	AcQMap™ High Resolution Imaging and Mapping System
DEVICE SHORT NAME	AcQMap™
DEVICE COMPONENTS	The AcQMap™ System consists of the following components: 
 
• The AcQMap™ 3D Imaging and Mapping Catheter (AcQMap™ Catheter)
 
• The AcQGuide™ Steerable Delivery Sheath
 
• The AcQMap™ Console
 
• The AcQMap™ Workstation
 
• The AcQMap™ Patient Electrode Kit
 

INDICATION FOR USE (INTENDED USE)	The AcQMap™ Imaging and Mapping System is intended for imaging and mapping of cardiac chambers, which will be utilized in the management of cardiac arrhythmias.
SPONSOR	Acutus Medical, Inc. [name] [name]
STUDY OBJECTIVE	To evaluate the incidence of device- and procedure-related safety, efficacy, and efficiency (6 and 12 month outcomes) when using the AcQMap™ as an imaging and mapping system for ablation of persistent atrial fibrillation (AF).
STUDY DESIGN	A prospective, single-arm, multi-center, multi-national, non-randomized, post-market study designed to provide clinical data regarding the use of the AcQMap™ System in the ablation of persistent atrial fibrillation.  Subject assessments will occur at screening, procedure, hospital discharge, 1, 3, 6, 9, and 12 months.  Data may be published at 6 and 12 months
PRIMARY MEASURABLE OBJECTIVE	The primary measurable objective is an analysis of the proportion of subjects who are free from device/procedure related Major Adverse Events (MAEs) that occur within the first 24 hours post-procedure. MAEs include any of the following: 
 
• Death
 
• Cardiac perforation/pericardial tamponade
 
• Cerebral infarct, transient ischemic attack (TIA), or systemic embolism
 

	
 
• Major bleeding
 
• Mitral or tricuspid valvular damage
 
• Other serious adverse device effects (SADEs) adjudicated by an independent Clinical Events Committee (CEC) as “probably related” to the AcQMap
 


SECONDARY MEASURABLE OBJECTIVES
	
Secondary measurable objectives include the following:
 
Safety Outcomes Measure
 
 
• Recording and analysis of all identified adverse events (AEs) and adverse device effects (ADEs) through 12 months post-procedure. Events will be adjudicated by an independent Clinical Events Committee (CEC) for severity and relationship to the AcQMap
 
 
Procedural Outcome Measures
 
 
• Analysis of the proportion of subjects with acute procedural (ablation) success defined as: 
 
- Conversion to sinus rhythm (with or without DC cardioversion) within 12 hours of the ablation procedure
 
- Procedural conversion to atrial flutter, atrial tachycardia or other organized supraventricular rhythm
 
 
 
 
Clinical Outcome Measures
 
 
• Analysis at 3, 6, 9, and 12 months post ablation (with a 24 hour continuous ECG monitor) of the proportion of subjects with freedom from documented episodes of AF lasting longer than 30 seconds. Analysis will include: 
 
- Freedom from AF/AT/AFL without anti-arrhythmic drugs (AADs)
 
- Freedom from AF/AT/AFL with AADs
 
- Freedom from AF/AT/AFL with a single procedure
 
- Freedom from AF/AT/AFL with multiple procedures
 
 
 

SAMPLE SIZE
	
Up to 125 subjects will be enrolled.
 
Up to 15 clinical sites in Europe.

STUDY CENTER AND LOCATION
	
TBD

PATIENT POPULATION
	
The patient population will consist of men and women between the ages of 18 – 80 years of age scheduled for an endocardial ablation of persistent atrial fibrillation (AF).
 
A potential study patient will be eligible for study enrollment only if all of the following inclusion and none of the exclusion criteria apply:
 
Inclusion Criteria
 
IC 1 Male or female between the ages of 18 and 80 years
 
IC 2 Currently scheduled for an ablation of persistent atrial fibrillation defined as AF lasting at least 7 days but no more

	
than 12 months without electrical cardioversion
 
IC 3 Willingness, ability and commitment to participate in baseline and follow-up evaluations for the full length of the study
 
IC 4 Willing and able to give informed consent
 
Exclusion Criteria
 
EC 1 In the opinion of the Investigator, any known contraindication to an AF ablation, TEE, or anticoagulation
 
EC 2 Any duration of continuous AF lasting longer than 12 months
 
EC 3 History of previous left atrial ablation or surgical treatment for AF/AFL/AT
 
EC 4 Atrial fibrillation secondary to electrolyte imbalance, thyroid disease, or any other reversible or non-cardiac cause
 
EC 5 Structural heart disease as described below: 
 
a. Left ventricular ejection fraction (LVEF) < 40% based on TTE within 6 months of enrollment
 
b. Left atrial size > 50 mm based on TTE within 6 months of enrollment
 
c. An implanted pacemaker or ICD
 
d. Previous cardiac surgery, ventriculotomy, or atriotomy (excluding atriotomy for CABG (see EC 5, j)),
 
e. Previous cardiac valvular surgical or percutaneous procedure, or prosthetic valve
 
f. Interatrial baffle, closure device, patch, or PFO occluder
 
g. Presence of a left atrial appendage occlusion device
 
h. Coronary artery bypass graft (CABG) or PTCA procedure within the last 6 months
 
i. Unstable angina or ongoing myocardial ischemia
 
j. Myocardial infarction within the previous six (6) months
 
 
 
EC 6 History of blood clotting or bleeding disease
 
EC 7 ANY prior history of documented cerebral infarct, TIA or systemic embolism
 
EC 8 Pregnant or lactating (current or anticipated during study follow up)
 
EC 9 Current enrollment in any other study protocol where testing or results from that study may interfere with the procedure or outcome measurements for this study
 
EC 10 Any other condition that, in the judgment of the investigator, makes the patient a poor candidate for this procedure, the study or compliance with the protocol (includes vulnerable patient population, mental illness, addictive disease, terminal illness with a life expectancy of

--	--

	less than two years, extensive travel away from the research center)
STUDY DURATION	Enrollment is anticipated to take approximately six (6) to eight (8) months. Post-procedure follow up will occur at hospital discharge, 1, 3, 6, and 12 months. The total study duration is anticipated to be approximately 18 months.
STATISTICAL METHODS AND ANALYSIS SUMMARY	
The primary outcome measure for the study is the primary safety objective, defined as the proportion of subjects who are free from device/procedure related Major Adverse Events (MAEs) that occur within the first 24 hours post-procedure. Subjects who remain free from such device/procedure related MAEs will be considered a success with respect to the primary safety objective, and subjects who experience at least one such MAE will be considered a primary safety failure.
 
The analysis of the primary safety objective will be performed on the treatment population, which will include all enrolled subjects who complete a procedure up to the point the AcQMap catheter is deployed in the left atrium. The number and proportion of subjects in the treatment population who are primary safety successes will be computed, along with a 95% exact binomial (i.e., Clopper-Pearson) confidence interval on the proportion.
 
Descriptive statistics will be applied to all other outcome measures.

FOLLOW-UP EVALUATIONS	See Table Below

**Table 1: Schedule of Events**

	Screening  & Baseline	Procedure	Discharge	7 Days (± 3 days) Phone Contact	1-month (± 7 days)	3-month (± 14 days)	6-month (± 30 days)	9-month (± 30 days)	12-month (± 30 days)
CIP Informed Consent	X								
Medical History	X								
History & Physical Exam	X	X	X		X	X	X		X
Medications	X	X	X		X	X	X		X
Transthoracic Echo (TTE)	X (within 6 months)								X
Trans Esophageal Echo (TEE)		X (within 72 hours)							
Adverse Events		X	X	X	X	X	X		X
12-lead ECG	X	X	X		X	X	X		X
Labs	X								
HCG (female patients)	X								
Patient Reported Outcome Measures (AFEQT)	X				X	X	X		X
24-hour Continuous ECG Monitor Recording							X	X	X

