### Clinical Outcome Measures

- Analysis at 3, 6, 9, and 12 months post ablation (with a 24 hour continuous ECG monitor) of the proportion of subjects with freedom from documented episodes of AF lasting longer than 30 seconds. Analysis will include:
  - Freedom from AF/AT/AFL without AADs
  - Freedom from AF/AT/AFL with AADs
  - Freedom from AF/AT/AFL with a single procedure
  - Freedom from AF/AT/AFL with multiple procedures

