#### **7.4.3 Visits at One, Three, Six, and Twelve Months**

The following evaluations will be performed during each clinic follow-up visit. Data will be recorded on the Follow-Up eCRFs.

- History and Physical exam (including neurological assessment)
- Medication history
- Adverse events assessment
- 12-lead electrocardiogram
- Echocardiogram (TTE at 12 months only, for comparison to baseline)
- AFEQT Questionnaire (completed prior to visit)
- 24-hour continuous monitor (3, 6, 9, and 12 months)
  - Since the 24-hour continuous monitor at 9-months does not coincide with a follow-up visit, the subject will be instructed how and when to wear the recording device. Once the recording is completed, the device will be returned to the study site and the results of the recording will be entered into an eCRF.

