#### Arrhythmia Recurrence beyond the Blanking Period

Development of AF/AFL/AT beyond the blanking period should first be documented with an ECG or a 24-hour continuous ECG monitor. Recurrence of an arrhythmia will be recorded on the eCRF as part of the continued management process of the subject in follow-up. These will be documented at unscheduled or routine (three-, six- and twelve-month) follow up visits.

Treatment should follow the Investigator's standard of care and may include DCCV, AAD administration or repeat ablation (retreatment procedure). Use of a DCCV is recommended prior to an ablation as many of these arrhythmias may be self-limited. One retreatment is allowed and may only occur in the time range from day 91 through day 270 post-ablation.

In a retreatment procedure, the AcQMap System should be used following the same protocol as the index procedure. Documentation of the retreatment will be on the procedure retreatment eCRF form. Follow-up visits will restart using the same schedule as with the index procedure (7-day call, 1, 3, 6 months); however, the study completion date (12 months from the index procedure) will not change.

[figure not shown]
**Hospital admissions and clinic visits to treat these arrhythmias (cardioversion, in-patient medication change and ablation) will not constitute an SAE but will be reported as an additional intervention to the management of the persistent AF.** In the event the subject suffers an untoward or unanticipated complication as a result of the arrhythmia (i.e. thrombotic event, pulmonary edema etc.), an adverse event reporting will occur and be adjudicated by the Clinical Events Committee in accordance with the CEC Charter.

Screening, procedure and follow-up visits are outlined in Table 2 and a flow diagram of visits is pictured in Figure 10.

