### 1.2 Study Procedures

Subject assessments will occur at screening, procedure, hospital discharge, one, three, six, nine, and 12 months. A follow up phone call will also occur seven days post-procedure.

Inclusion and exclusion criteria will be assessed prior to enrollment and during the screening period up through the pre-procedure required transesophageal echocardiogram (TEE). Assessments performed during screening will include subject demographics, medical history, physical exam findings, transthoracic echo (TTE) results (within previous six months), clinical laboratory exams, electrocardiograms (ECGs), the Atrial Fibrillation Effect on Quality of Life (AFEQT) questionnaire and the aforementioned TEE.

Subjects who meet all inclusion and exclusion criteria will be enrolled into the study and will proceed to receive an ablation procedure. Prior to hospital discharge, the following post-procedure evaluations will be completed: physical exam, 12-lead ECG, collection of concomitant medications and reporting of all adverse events. A phone call will occur seven days following hospital discharge to review concomitant medications, adverse events, and scheduled follow up visits.

Follow up clinical visits will occur at one, three, six, and 12 months. The following evaluations will be performed:

- History and physical exam (including neurological assessment)
- Medication history
- Adverse events assessment
- Vital Signs
- 12-lead electrocardiogram
- Echocardiogram (TTE at 12 months only, for comparison to baseline)
- AFEQT Questionnaire (completed prior to the clinic visit)
- 24-hour continuous monitor (three, six, nine, and 12 months post ablation procedure)
  - Since the 24-hour continuous monitor at nine months does not coincide with a follow-up visit, the subject will be instructed how and when to wear the recording device. Once the recording is completed, the device will be returned to a core lab. Results will be compiled and reported to the site and Sponsor. Results of the recording will be entered into an electronic case report form (eCRF).

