### **24-Hour Holter Monitor**

A 24-Hour Holter monitor of heart rhythm will be completed at three, six, nine, and 12 months. The number and percent of subjects with each heart rhythm will be reported by time point. The Holter data will be listed along with the 12-Lead ECG data.

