#### 5.1.2 Description of Secondary Effectiveness Objectives

Secondary measurable effectiveness objectives include the following, which are divided into procedure outcome measures and clinical outcome measures.

The **procedure outcome measures** are:

- Proportion of subjects with acute procedural (ablation) success defined as:
  - Conversion to sinus rhythm (with or without direct current cardioversion [DCCV]) within 12 hours of the procedure
  - Procedural conversion to atrial flutter, atrial tachycardia or other organized supraventricular rhythm
- Procedure fluoroscopy time
- Ablation time to complete PVI
- Ablation time for non-PVI ablation
- Ablation time for right atrial ablation
- Number of DCCV completed during the procedure

The **clinical outcome measures** are:

- Proportion of subjects with freedom from documented episodes of AF/AT/AFL lasting longer than 30 seconds, based on the 24-hour continuous ECG monitor at three, six, nine, and 12 months post ablation. Analysis will include:
  - Freedom from AF/AT/AFL without AADs
  - Freedom from AF/AT/AFL with AADs
  - Freedom from AF/AT/AFL with a single procedure
  - Freedom from AF/AT/AFL with multiple procedures
- Improvement of left atrial (LA) size at 12 months compared to baseline
- Number of repeat ablation procedures in follow-up period from day 91-270 (i.e., from three months to nine months)
- Number of DCCV in first 90 days post-ablation
- Number of DCCV from day 91-365 (i.e., from three months to 12 months)
- Changes in patient reported outcomes (PROs) in the follow-up period, based on the AFEQT questionnaire

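### Schedule Tables 1 and 2 leave the 3-month 24-hour monitor cell blank, although the objectives, Protocol 7.4.3 and the SAP require a 3-month recording

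*Combined protocol and SAP*

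**What the plan says.** **Schedules.** Protocol Table 1 (synopsis) and Table 2 (section 7.5) each carry a row "24-hour Continuous ECG Monitor Recording". It has three marks, at 6, 9 and 12 months, and the 3-month cell is empty in both. Sites are sent to these tables: the synopsis entry for follow-up evaluations reads "See Table Below", and section 7.5 states "Screening, procedure and follow-up visits are outlined in Table 2".

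**Text.** Protocol 7.4.3 lists "24-hour continuous monitor (3, 6, 9, and 12 months" among the follow-up evaluations. The clinical outcome measures in Protocol 6.2.2 specify "Analysis at 3, 6, 9, and 12 months post ablation (with a 24 hour continuous ECG monitor", and the synopsis says the same. SAP 1.2 gives "24-hour continuous monitor (three, six, nine, and 12 months post ablation procedure". SAP 4.2.2 says "A 24-Hour Holter monitor of heart rhythm will be completed at three, six, nine, and 12 months". SAP 5.1.2 defines the freedom endpoint as "based on the 24-hour continuous ECG monitor at three, six, nine, and 12 months post ablation", and 5.2.2 repeats this with an exact 95% interval for each proportion.

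**Missing recordings.** SAP 2.3 substitutes the same visit's 12-lead ECG for a missing Holter at 3, 6 and 12 months, and plans statistics both with and without the substitution. The SAP revision history (Version 1.1 to 2.0, item 5) records a footnote to Tables 7 and 35 that names the monitor as the source, with 12-lead imputation where monitor data are unavailable. The 1.0 to 1.1 entries identify Table 7 as the AF/AT/AFL freedom table.

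**The concern.** The protocol gives a site two different answers on whether to record a 24-hour monitor at 3 months. A recording that was never made cannot be recovered later.

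Both schedules do mark a 12-lead ECG at 3 months, so SAP 2.3 would have something to substitute. The substitute measures something else. The endpoint is the absence of any episode over 30 seconds across 24 hours, whereas a 12-lead ECG shows the rhythm at one moment. If sinus rhythm on that ECG is scored as free, the error runs one way, towards more freedom. A reader of the 3-month rate would not know how much of it came from monitoring unless the number imputed is shown.

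**Working it through.** **1. The plan's own design figure.** Protocol 8.4 and SAP 1.3 give N = 125 for a 95% Clopper-Pearson half-width of 3.89% at an observed 96.0%. For 120/125 the exact interval is 90.91% to 98.69%, half-width 3.888%. It reproduces, and the present point does not depend on it.

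**2. Is the 3-month cell really blank?** The tables have nine visit columns: screening and baseline, procedure, discharge, 7 days, then 1, 3, 6, 9 and 12 months.

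| Row | Marked at | Agrees with the text? |
|---|---|---|
| 12-lead ECG | screening, procedure, discharge, 1, 3, 6, 12 months | yes (SAP 4.2.2) |
| AFEQT | screening, 1, 3, 6, 12 months | yes (Protocol 7.4.3) |
| 24-hour monitor | 6, 9, 12 months | no, 3 months is absent |

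The neighbouring rows align with the text and both tables show the same gap, so a reading fault is unlikely. Even without column alignment, three marks cannot cover four required recordings.

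**3. Shift of the imputed rate.** Let s be the share of subjects without a 3-month recording. Let P be the share who would show an episode over 30 seconds on 24-hour monitoring, and d the share of those whose visit ECG shows the arrhythmia. Assume that omission is unrelated to rhythm and that imputed sinus rhythm is scored as free. Then

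upward shift = s × P × (1 − d).

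The documents give none of the three. For s, take one site at the cap in Protocol 6.4: 25/125 = 0.20. Assume P = 0.20 to 0.40 and d = 0.30 to 0.90.

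- Lowest: 0.20 × 0.20 × 0.10 = 0.004, or 0.4 points.
- Middle: 0.20 × 0.30 × 0.50 = 0.030, or 3.0 points.
- Highest: 0.20 × 0.40 × 0.70 = 0.056, or 5.6 points.

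**4. Precision of the complete-case rate** (exact 95% intervals near 70% freedom).

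- All 125 recorded: 88/125, 61.6% to 78.2%, half-width 8.3 points.
- 25 not recorded: 70/100, 60.0% to 78.8%, half-width 9.4 points.

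**5. The two versions side by side.** Of 25 unrecorded subjects, 25 × 0.30 = 7.5 would have arrhythmia. If the ECG shows half of these, about 4 are detected and 21 are in sinus rhythm. Holter-only is 70/100 = 70.0% (60.0 to 78.8). Imputed is (70 + 21)/125 = 91/125 = 72.8% (64.1 to 80.4). The imputed interval is the narrower, although 25 of its 125 subjects were never monitored.

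**The case against.** The strongest reply is that section 7.4.3 is the instruction and names month 3, while section 7.5 only outlines the visits by pointing to Table 2. Blank eCRF items are queried (Protocol 11.8), monitors check compliance (11.11) and sites are trained on the protocol (11.15). These safeguards make repeated omission at a site less likely. They cannot restore a recording already missed, so the contradiction still needs to be removed.

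It is also fair to say that nothing is hidden. SAP 2.3 plans both versions, and the revision history (Version 1.0 to 1.1, item 3) describes Table 22 as split into 12-lead results, Holter results including 3 months, and results after imputation. That table shows rhythm rather than freedom, so the labelling of the freedom tables remains open.

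The consequence is limited. The endpoint is secondary and descriptive. Protocol 5.2 defines success for the historical comparison at 6 and 12 months, where both tables mark the monitor. The 3-month window of ±14 days straddles the end of the 90-day blanking period, which makes this visit less informative.

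Three stronger readings are tempting, and the documents do not support them.

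- **The 3-month rate will rest wholly on ECGs.** That would need every site to set 7.4.3 aside. It would also need the same gap in the companion study CL-AF-001, whose schedule is not among the documents although N = 125 covers both studies.
- **The SAP has no rule for scoring an imputed sinus rhythm.** No rule appears in the supplied text, but the table shells in Appendix B were not supplied and may contain one.
- **One version is the less biased and should lead.** That depends on why recordings are missing and on ECG detection, and the documents give neither.

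**Conclusion.** The inconsistency stands as written: two schedule tables omit a 3-month recording that the objectives, Protocol 7.4.3 and the SAP require. The effect on results is conditional. It arises only where a site follows the tables, and the upward tendency only if imputed sinus rhythm counts as free. With one capped site omitting the recording, the imputed 3-month rate would be 0.4 to 5.6 points too high on the assumed arrhythmia and detection ranges, and the complete-case half-width would grow by about 1 point (9.4 − 8.3 = 1.1). The 20% is an illustration, not a forecast. The primary safety objective and the sample size are untouched. Severity is low to moderate.

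**What to change.** 1. Reconcile the 24-hour monitor row of Tables 1 and 2 with Protocol 7.4.3, the objectives and the SAP, so that sites, the endpoint definition and the analysis state the same set of recordings.
2. In the freedom tables, show the Holter-only and ECG-imputed rates side by side, with the number imputed at each visit.
3. Label any result that rests on the 12-lead ECG alone as ECG rhythm, not as freedom on a 24-hour monitor, and make the table footnote match.

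The cost is a correction to one row in two tables, extra columns in the freedom tables and a revised footnote. Both rates are already planned in SAP 2.3, so no new analysis is needed. The first item is worth doing before subjects reach their 3-month visit, because only then can it prevent lost recordings.

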## **4 ABBREVIATIONS**

3D	Three Dimensional
AAD	Anti-Arrhythmic Drug
ACT	Activated Clotting Time
ADE	Adverse Device Effect
AE	Adverse Event
AF	Atrial Fibrillation
AFEQT	Atrial Fibrillation Effect on Quality of Life
AFL	Atrial Flutter
AT	Atrial Tachycardia
CABG	Coronary Artery Bypass Grafting
CEC	Clinical Events Committee
CIP	Clinical Investigational Plan
CMP	Clinical Monitoring Plan
CPM	Clinical Project Manager
CRA	Clinical (or Contract) Research Associate
CRO	Contract Research Organization
CRF	Case Report Form
CTA	Clinical Trial Agreement
DCCV	Direct Current Cardioversion
DCF	Data Clarification Form
DMP	Data Management Plan
EC	Ethics Committee
EU	European Union
eCRF	Electronic Case Report Form
ECG	Electrocardiogram
EGM	Electrogram
EMR	Electronic Medical Record
FDA	Food and Drug Administration
GCP	Good Clinical Practices
ICF	Informed Consent Form
ICH	International Conference on Harmonisation
IA	Investigator Agreement
ICD	Implantable Cardioverter Defibrillator
IFU	Instructions For Use
IM	Investigator Meeting
IMV	Interim Monitoring Visit
ISF	Investigator Site Files
ISO	International Organization for Standardization

LA	Left Atrium
LFU	Lost to Follow-Up
LVEF	Left Ventricular Ejection Fraction
MAE	Major Adverse Event
PAF	Paroxysmal Atrial Fibrillation
PFO	Patent Foramen Ovale
PI	Principal Investigator
PROs	Patient Recorded Outcomes
PTCA	Percutaneous Transluminal Coronary Angioplasty
PV	Pulmonary Vein
PVI	Pulmonary Vein Isolation
QAP	Quality Assurance Procedure
RMV	Routine Monitoring Visit
SADE	Serious Adverse Device Effect
SAE	Serious Adverse Event
SC	Study Coordinator
SD	Standard Deviation
SIV	Site Initiation Visit
SQV	Site Qualification Visit
SOP	Standard Operating Procedure
SVT	Supraventricular Tachycardia
TEE	Transesophageal Echocardiogram
TIA	Transient Ischemic Attack
TMF	Trial Master File
TS	Trans-septal Puncture
TTE	Transthoracic Echocardiogram
UADE	Unanticipated Adverse Device Effect
USFDA	United States Food and Drug Administration
WACA	Wide Area Circumferential Ablation

